Specific Aim 1: The overall goal for this aim is to assess the population level pharmacokinetic-pharmacodynamic (PK-PD) model for propofol sedation in *PD patients (who have BG pathology) in contrast to a control group (essential tremor, ET, who do not have BG pathology)*. The PK-PD model will be used to predict the time course of plasma and effect site concentration of propofol and establish differential anesthetic sensitivity profiles. This assessment will be done during battery placement surgeries for individuals already implanted with DBS electrodes.

Specific Aim 2: These experiments will be performed during the initial DBS implantation surgery. The overall goal for this aim is to assess neural correlates, with specific attention to network parameters/states, during LOC/LOR and ROC/ROR using direct, high-resolution invasive recordings from the basal ganglia (GPi/GPe) and frontoparietal cortices in humans. *There is only one study group in this aim – PD patients (no stimulation of GPi/GPe).*

Specific Aim 3a: These experiments will be performed during the DBS generator exchange surgeries, as in Aim 1. All study participants will have PD in this set of experiments and results will be compared across *experimental cohorts (GPi vs GPe stim)* as well as to PD patients anesthetized with propofol off stimulation (from Aim 1). During data analysis, the rater will be blinded to stimulation assignment.

Specific Aim 3b: These experiments will be performed during the initial DBS implantation surgery. Recordings and behavioral assessments will be made during both induction and emergence of anesthesia with *either GPi or GPe stimulation*, comparing results with those acquired in Aim 2 (no stimulation). As in Aim 3a, the rater will be blinded to stimulation assignment.

4. Research Plan / Description of the Research Methods:

4.a. Provide a comprehensive narrative describing the research methods.

- 1) Provide the **order in which tests/procedures will be performed**,
- 2) Provide the **setting** for these events and a description of the **methods used to protect privacy** during the study.
- 3) Provide the **plan for data analysis** (include as applicable the **sample size calculation**)

Please respond to all components of this item, or clearly indicate which components are not applicable.

Some information in responses below is taken from grant protocol section 3 "Approach". See figures referenced and citations in grant protocol.

RESEARCH METHODS

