PK-PD Model Fitting. The pharmacodynamic responses for both behavioral endpoints will be modeled with a sigmoidal E_{max} function: $Fraction_{responsive} = 1 - C_e^{\gamma} / (C_{e50}^{\gamma} + C_e^{\gamma})$; Where Ce is the effect site concentration, Ce₅₀ is the effect site concentration at which half of the population is no longer responsive, and γ is the Hill coefficient governing the slope of the sigmoid. Fitting will be done using NONMEM (ICON Development Solutions) and parameter estimation. Comparison of Ce₅₀ values between PD and ET populations will be made using 95% confidence limits on the resulting parameter fits. Additional exploratory analyses of the model will attempt to account for heterogeneity in the PD population by constructing candidate models that nest the PD effect by both UPDRS scores and covariates of cognitive function (MoCA), utilizing a drop of corrected Akaike Information Criterion (AIC) by 20 points as a threshold for a significant improvement from adding a parameter to the model.

Specific Aim 2:

We will temporally correlate the evolution of behavioral measures of LOC/LOR (including loss of spontaneous movement and loss of movement to command, with digital synchronization with neurophysiological recordings through digital event recording) with I changes in GPi vs GPe pallidocortical circuits. Techniques outlined in LFP analyses above will be implemented to complete assessment.

Specific Aim 3a:

Statistical analysis pipeline outlined in Aim 1 will be replicated in Aim 3a.

Specific Aim 3b:

Recordings and behavioral assessments will be compared to results acquired in Aim 2. Techniques outlined in LFP analyses above will be implemented to complete assessment.

SAMPLE SIZE

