Aim 3a: We estimate our sample size using a Monte Carlo simulation based on predicted differences in propofol sensitivity as defined in prior studies,^{47, 48, 57, 75} which suggest a 20% difference in Ce50 with 20% intersubject variability and an additive measurement error. We performed the Monte Carlo simulation by constructing two population response curves from N patients whose response to propofol was determined by the sigmoidal Emax model while varying only the Ce50 between the populations. The nonlinear fitting was performed for both populations and this process was repeated 1000 times, with the fraction correctly identifying the underlying difference in the model used as our power estimate. N was then incremented until 80% power was obtained, which required approximately 24 patients per arm (total of 48 patients). Similar studies have targeted enrollments of 18-31 subjects per arm.^{47, 48, 76} To account for an estimated 20% dropout rate or protocol error, we plan to recruit a total of 58 subjects. Data collection will occur at UTSW and UCLA.

Aim 3b: Our experiments are purposefully designed to ensure proper power and that experiments can be completed within intraoperative time constraints. Using our prior LFP recordings in PD as well as the published literature^{43, 78, 79}, we conducted a power analysis based on average α/β power modulation between rest and anesthetized state observation (Figure 1). Power analysis indicates a total of 16 patients is required to achieve significant results (one-sample t-test with $d=0.75$, $p=0.8$, $\alpha=0.05$). To account for an estimated 20% dropout rate or protocol error, we plan to recruit at least 20 subjects. Data collection will occur at UTSW and UCLA.

Form A

IRB #	STU 2021-0396
-------	---------------

4.b. List of the study intervention(s) being tested or evaluated under this protocol

☐ **N/A** - this study does not test or evaluate an intervention. [Skip to item 4.d.](#)

#	Study intervention(s) being tested or evaluated under the protocol	Affiliate	Local Standard Practice?
	Add or delete rows as needed	Place a check next to institution(s) where the intervention will be performed	Indicate whether the intervention is considered acceptable practice locally for applicable institutions
1	Propofol administration	 UTSW	 Yes
		 PHHS	 Yes

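### Aim 3b borrows Aim 2's one-sample sample size, so the stated 80% power does not apply to its comparison of stimulated with unstimulated patients

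*Combined protocol and SAP*

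**What the plan says.** **Sample size.** In Section 4.a (Sample Size), the Aim 3b paragraph has the same wording as the Aim 2 paragraph. It states its basis as "we conducted a power analysis based on average α/β power modulation between rest and anesthetized state observation" and its test as "one-sample t-test with $d=0.75$, $p=0.8$, $\alpha=0.05". It concludes "Power analysis indicates a total of 16 patients is required to achieve significant results", raised to at least 20 for 20% dropout or protocol error.

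**Comparison.** Section 1 gives Aim 3b's primary outcome as neurophysiological signals, looking at how their evolution differs with and without DBS. Section 3, Specific Aim 3b, has patients recorded under GPi or GPe stimulation, "comparing results with those acquired in Aim 2 (no stimulation". The Aim 3b entry under Data Analysis in Section 4.a agrees: "Recordings and behavioral assessments will be compared to results acquired in Aim 2". Aim 2 is a single group of PD patients without stimulation. The statistical analysis paragraph plans t-tests between conditions.

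**Aim 3a.** Its sample-size paragraph repeats Aim 1's simulation, including the reference to prior studies "which suggest a 20% difference in Ce50 with 20% intersubject variability and an additive measurement error".

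**The concern.** A one-sample test on the rest-to-anesthetized change asks whether propofol alters the signal within a patient. That is Aim 2's question. Aim 3b asks whether stimulation alters the change, and it answers by comparing two sets of patients. A difference between two independent means has a larger standard error than a single mean from the same number per group, so the sample size for the first question does not carry over to the second.

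The Aim 3b paragraph presents the experiments as designed to be properly powered. Patients in this aim have research-only cortical strips placed and about 40 extra minutes in the operating room, and Section 4.c lists no benefit from the stimulation. The power claim is part of the justification for that, and it is unsupported for the comparison the aim makes. The plan does not say how a non-significant result would be interpreted. Next to a stated 80%, though, it could easily be taken as evidence that stimulation has no effect.

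**Working it through.** **Inputs from the plan:** d=0.75, α=0.05, power 0.80, 16 evaluable and at least 20 recruited in each of Aims 2 and 3b.

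**Inputs assumed here:**
- The test is two-sided. The plan does not say, but the two-sided test reproduces 16, whereas a one-sided test would need 13.
- d=0.75 also holds for the between-group difference. The plan gives it only for the within-patient change.
- Where one site is considered alone, GPi and GPe are split evenly. The plan gives no allocation.
- There is no multiplicity adjustment.

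**Step 1: reproduce the plan's figure.** One-sample t-test, df = n − 1, noncentrality = d√n. With n=16: df = 15, noncentrality = 0.75 × 4 = 3.00, power = 0.801. For dropout, 16 / 0.8 = 20. Both stated numbers are correct for this test.

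**Step 2: power for between-group contrasts.** Two-sample t-test, df = n₁ + n₂ − 2, noncentrality = d√(n₁n₂/(n₁+n₂)). For 16 v 16: 0.75 × √(256/32) = 0.75 × √8 = 2.12, df = 30, power 0.537. The other rows follow in the same way.

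| Contrast | n₁ v n₂ | Noncentrality | df | Power at d=0.75 | d detectable with 80% power |
|---|---|---|---|---|---|
| All stimulated v Aim 2 | 16 v 16 | 2.12 | 30 | 53.7% | 1.02 |
| All stimulated v Aim 2 | 20 v 20 | 2.37 | 38 | 63.7% | 0.91 |
| One site v Aim 2 | 8 v 16 | 1.73 | 22 | 38.1% | 1.27 |
| One site v Aim 2 | 10 v 20 | 1.94 | 28 | 46.4% | 1.12 |
| GPi v GPe, if tested | 8 v 8 | 1.50 | 14 | 28.7% | 1.51 |
| GPi v GPe, if tested | 10 v 10 | 1.68 | 18 | 35.5% | 1.32 |

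The 20 v 20, 10 v 20 and 10 v 10 rows suppose that every recruit is evaluable.

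**Step 3: sensitivity.**
- One-sided 5%: all stimulated v Aim 2 has 66.6% (16 v 16) or 75.3% (20 v 20), still below 80%.
- Smaller effect, d=0.53, 16 v 16, two-sided: 30.6%.
- Larger effect, d=1.06, 16 v 16, two-sided: 82.7%. The plan offers no basis for an effect of that size.

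**Step 4: what 80% at d=0.75 would need.** 29 evaluable per group (power 0.801), or 29 / 0.8 = 36.25, so 37 recruited per group. Enlarging Aim 3b alone is inefficient: with Aim 2 held at 16 evaluable it would need about 123 stimulated patients, and with Aim 2 at 20 about 51.

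**The case against.** The strongest objection is that d=0.75 belongs to a different quantity. It is the standardised within-patient change, so no power figure for the between-group contrast can be derived from the plan alone. This stands: the percentages above are conditional and true power is unknown. It does not rescue the stated 80%, which has no basis for this comparison under any effect size given in the plan. Nor is carrying d=0.75 over a harsh choice. On the change scale with the same standard deviation, it supposes that stimulation shifts the change by as much as the whole anesthetic effect.

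One could also read Section 1's description of Aim 3b, with or without DBS, as an on/off comparison inside the aim. The methods describe no off-stimulation run within an Aim 3b patient. If the 16 were instead divided into on and off groups, the test would still be two-sample, with about 8 per group.

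Three stronger readings are tempting but not supported:

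- *That the range starts at 29%.* This needs GPi against GPe to be an Aim 3b test. Section 3 states that contrast explicitly only for Aim 3a. For Aim 3b the named comparator is Aim 2.
- *That the plan has an arithmetic error.* It has none here, since 16 and 20 reproduce. The fault is a mismatch between test and design.
- *That Aim 3a shares the fault, or has an uncontrolled error rate over three groups.* Its 24 per arm already comes from a two-population simulation. With an even split of sites and Aim 1's 24 PD patients as the off-stimulation group, each pairwise contrast is 24 v 24, as simulated. Section 1 describes Aim 3a as two randomized arms, while Section 3 implies three groups. The inherited analysis compares 95% confidence limits on fitted parameters and specifies no set of pairwise tests or adjustment, so a familywise error figure would rest on tests the plan does not define.

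One point on Aim 3a remains. The 20% Ce50 difference is the shift Aim 1 expects between PD patients and patients without basal ganglia pathology. All Aim 3a patients have PD and the question is stimulation, so there the 20% is an assumption.

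**Conclusion.** The concern holds for Aim 3b. Its sample size answers Aim 2's within-patient question, and the stated 80% does not apply to stimulated versus unstimulated patients. The plan gives no effect size, allocation or power for that comparison.

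Assuming d=0.75 between groups and a two-sided 5% test, power for the stated contrast is about 54% with 16 v 16 evaluable and 64% with 20 v 20. With an even GPi/GPe split, one site versus Aim 2 has about 38% (46% with 10 v 20). GPi versus GPe, if it is tested at all, has about 29% (36% with 10 v 10). That the 80% is unsupported depends on none of these assumptions; only the size of the shortfall does. For Aim 3a the point is confined to the origin of the 20% difference.

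**What to change.** Keep the patient numbers and change the wording of Section 4.a (Sample Size).

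1. **Aim 3b.** Remove the one-sample power sentence. Name one primary contrast: all stimulated patients versus Aim 2 (with versus without DBS) on the rest-to-anesthetized change in α/β power. State that it is a two-sample, two-sided 5% comparison, with detectable effect at 80% power of d about 1.02 with 16 v 16 evaluable and 0.91 with 20 v 20.
2. **Site-specific contrasts.** State the intended GPi/GPe allocation. Report one site versus Aim 2, and GPi versus GPe if wanted, as estimates with confidence intervals. Under an 8:8 split the detectable d is about 1.27 and 1.51 respectively.
3. **Aim 3a.** State that the 20% Ce50 difference is an assumption for a stimulation effect, carried over from Aim 1, and not a figure from prior studies of stimulation.

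This costs protocol wording only, with no extra patients and no change to procedures. The downside is a less favourable stated power.
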